6.13. Bioanalytical and Pharmacokinetic/Pharmacodynamic Methods

PK/PD analyses to address secondary and exploratory objectives of this study will be described by Lilly in separate PK/PD analysis plans. Conduct of the PK/PD analyses will be the responsibility of Eli Lilly and Company.

The PK/PD analyses will be initiated up to approximately three weeks before the planned database lock dates. All analyses will be performed by unblinded Lilly PK personnel, who are unblinded to subject treatment assignments to support dose adjustments, as specified in protocol Section 9.5. Results from the PK/PD analyses will not be shared with site or blinded study team personnel prior to the respective database lock.

6.14. Safety Analyses

All safety evaluations will be based upon the Safety Population as defined in Section 6.2.

Any statistical comparisons for safety data will be performed only between the “All LY3074828” treatment group and Placebo. No pairwise comparisons between LY3074828 induction treatment arms will be performed. Pairwise comparison of LY3074828 maintenance treatment arms will be performed (no comparison to placebo). No multiplicity control procedure will be performed for these tests of safety data.

Safety and tolerability will be evaluated in terms of treatment-emergent AEs (TEAEs), AEs leading to permanent discontinuations of study drug, SAEs, deaths, changes in clinical laboratory test results, and vital signs. These measures will be analyzed for each dose group and combined LY3074828 groups, separately for each study part, as well as across study parts for key summaries.

For all quantitative safety analyses, baseline is defined as the last non-missing assessment recorded on or prior to the date of first study drug injection at Week 0 (Visit 2). However, placebo patients who enter the Extension Period will have their baseline reset. Their new baseline will be defined as the last non-missing assessment on or prior to the date of first injection of study treatment at Week EW0 (Extension Visit 1).

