12.2.8. Safety Analyses

Safety will be assessed by evaluating all reported AEs and changes in laboratory analytes, ECGs, and vital signs (including body weight).

Duration of exposure to therapy will be calculated for each subject and summarized by treatment group.

AEs will be coded according to the *Medical Dictionary for Regulatory Activities* and summarized by system organ class, preferred term, severity, and relationship to investigational product. A TEAE is defined as an event that first occurred or worsened in severity after baseline. In the analysis of TEAEs during the induction period, all preexisting conditions recorded at screening (Visit 1) and any on-study AEs recorded at or before baseline (Visit 2) will be used as baseline. In the analysis of TEAEs during the maintenance period, any on-study AEs recorded at Week 12 will be used as baseline. The induction period and the maintenance period will be analyzed separately. For each event classification term, the number of subjects experiencing a TEAE with that classification term will be tabulated. Treatment-related TEAEs are defined as events that are indicated by the investigator on the CRF to be related to treatment. If a subject reports the occurrence of a particular event more than once, the most severe of those events will be included in the summary tables of TEAEs, and the most severe of the most related of those events will be included in the summary tables of treatment-related events. TEAEs of interest will be presented.

Additional safety parameters include laboratory test results, ECGs, and vital-sign measurements. The baseline for computing the change in safety variables for the induction period will be data collected at or before dosing on Visit 2; the baseline for the maintenance period will be the last value collected during the induction period. The parameters will be listed and summarized with standard descriptive statistics. Change from baseline will also be summarized by randomized treatment.

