6.14.4. Clinical Laboratory Evaluation

Laboratory evaluations will be summarized and analyzed for the following periods:

- Induction Period,
- Maintenance Period,
- Extension Period (including Extension Induction and Extension Maintenance)

Laboratory tests include all planned analytes as defined in the protocol, excluding those collected in a reflex manner (only collected under certain circumstances).

Values at each visit (starting at randomization) and change from baseline to each visit for laboratory tests will be displayed in box plots (notched box for each treatment with outliers displayed) for patients who have both a baseline and a result for the specified visit. Individual measurements outside of reference limits (defined by the performing laboratory) will also be displayed using distinct symbols overlaying the box plot. Baseline will be the last non-missing observation in the screening period. Original-scale data will be used for the display. Unplanned measurements will be excluded. Displays using both SI and U.S. conventional units will be provided (when different). The following summary statistics will be included in a table below the box plot: N, mean, standard deviation, minimum, Q1, median, Q3, and maximum. Box plots will be used to evaluate trends over time and to assess a potential impact of outliers on central tendency summaries.

Change from baseline to last observation will also be summarized within the box plot of changes (rightmost column) for patients who have both baseline and at least one post-baseline result. Baseline will be the last non-missing observation in the screening period. The last non-missing observation in the treatment period will be used as the last observation. Original-scale data will be used. Unplanned measurements will be excluded. A p-value will be included in the summary statistics at the bottom of the box plot for this assessment, using an ANCOVA model containing terms for treatment and the continuous covariate of baseline measurement.

For quantitative laboratory analyte measurements, 3-panel displays that include a scatterplot, a shift table, and a shift to high/low table will be created. Specifically, for each measurement, both a 3-panel display assessing low values and a 3-panel display assessing high values will be created.

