6.14.5. Vital Signs and Other Physical Characteristics

Vital signs include systolic blood pressure, diastolic blood pressure, pulse, and temperature. Physical characteristics include weight and BMI.

Vital signs and physical characteristics will be summarized and analyzed for the following periods:

- Induction Period
- Maintenance Period
- Extension Period

Vital sign and physical characteristic results will be provided in a by-patient listing.

BMI will be calculated using the following formula.

$$\text{BMI (kg/m}^2\text{)} = \text{weight (kg) divided by the square of the height (m).}$$

Values at each visit (starting at randomization) and change from baseline to each visit for vital signs and physical characteristics will be displayed in box plots (notched box for each treatment with outliers displayed) for patients who have both a baseline and a result for the specified visit. Individual measurements outside of reference limits will also be displayed using distinct symbols overlaying the box plot. Baseline is defined as the last non-missing assessment recorded on or prior to the first study drug injection at Week 0 (Visit 2). Original-scale data will be used for the display. Unplanned measurements will be excluded. The following summary statistics will be included in a table below the box plot: N, mean, standard deviation, minimum, Q1, median, Q3, and maximum. Box plots will be used to evaluate trends over time and to assess a potential impact of outliers on central tendency summaries.

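### SAP 6.14 keeps the Week 0 safety baseline through maintenance, where the protocol uses the last induction value, and SAP 6.18 does not declare the change

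*SAP*

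**What the plan says.** **Protocol 12.2.8**, repeated in the synopsis, gives two safety baselines. For induction: "The baseline for computing the change in safety variables for the induction period will be data collected at or before dosing on Visit 2". For maintenance: "the baseline for the maintenance period will be the last value collected during the induction period".

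**SAP 6.14** gives one general rule: "For all quantitative safety analyses, baseline is defined as the last non-missing assessment" on or before the first dose at Week 0 (Visit 2). It makes one exception: "However, placebo patients who enter the Extension Period will have their baseline reset", with the new baseline taken on or before the first dose at Extension Visit 1. Nothing is reset at re-randomisation into maintenance. The same section plans the safety measures "separately for each study part, as well as across study parts for key summaries".

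**SAP 6.14.4** (laboratory) covers induction, maintenance and extension. For change from baseline it says, twice: "Baseline will be the last non-missing observation in the screening period". Its shift tables compare the minimum or maximum in the screening period with the minimum or maximum in the treatment period. SAP 6.14.4.1 likewise takes the maximum hepatic baseline from the screening period.

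**SAP 6.14.5** (vital signs and weight) covers the same three periods. It repeats the Week 0 rule for change from baseline and uses screening-period extremes for treatment-emergent high and low results.

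**SAP 6.18** lists two departures from the protocol, the categorical analysis method and the medication summaries, and says that there are no others.

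**The concern.** The two documents give different changes from baseline for the same patient at the same maintenance visit, and neither acknowledges the other. A programmer following the SAP would report, under a maintenance heading, a change that began before the first induction dose. Patients re-randomised into maintenance are by definition induction responders to LY3074828 who had infusions planned at Weeks 0, 4 and 8. Any movement in a laboratory value, vital sign or weight during those weeks would appear in the summary of the maintenance regimen.

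This matters mainly for description. Maintenance has no planned safety comparison with placebo (SAP 6.14), so readers will lean on within-arm changes, shift tables and treatment-emergent rates to judge each regimen.

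**Working it through.** The plan gives no figure to reproduce. The check compares the rules and then does the visit-day arithmetic.

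**Inputs (Protocol Attachment 1, nominal days).** Visit 2 is Day 1. Visit 7, the last induction visit, is Day 78 to 85. Maintenance visits with chemistry and haematology include Week 16 (Day 113), Week 52 (Day 365) and Week 104 (Day 728). Chemistry, haematology, vital signs and weight are all scheduled at Visit 7. Laboratory tests are not scheduled at Visit 8.

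**Step 1: extra time in the SAP change.** 78 − 1 = 77 days and 85 − 1 = 84 days, so 11.0 to 12.0 weeks.

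**Step 2: share of the interval that is induction.**

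| Visit | Days from Visit 2 (SAP) | Days from Visit 7 (protocol) | Induction share |
|---|---|---|---|
| Week 16 | 113 − 1 = 112 | 28 to 35 | 77/112 to 84/112 = 69% to 75% |
| Week 52 | 365 − 1 = 364 | 280 to 287 | 77/364 to 84/364 = 21% to 23% |
| Week 104 | 728 − 1 = 727 | 643 to 650 | 77/727 to 84/727 = 11% to 12% |

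These are shares of time, not of effect. The documents give no size for the induction change.

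**Step 3: what the within-arm change contains.** For a maintenance visit m,

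Y(m) − Y(V2) = [Y(V7) − Y(V2)] + [Y(m) − Y(V7)].

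The SAP reports the left side; the protocol reports only the last bracket. With assumed induction shifts of 0.1, 0.3 or 0.5 SD and no change in maintenance, both active arms show 0.1, 0.3 or 0.5 SD under the SAP and 0 under the protocol.

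**Step 4: the contrast between regimens.** Q4W and Q12W are formed by re-randomisation after induction, so the first bracket has the same expectation in both arms and cancels. If Q4W adds an assumed 0.2 SD in maintenance and Q12W adds none, then with an induction shift of 0.3 SD the arms show 0.5 and 0.3 under the SAP and 0.2 and 0 under the protocol. The difference is 0.2 under both rules.

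**Step 5: categorical output.** The baseline here is an extreme from the screening period, with no separate window for maintenance. Two errors follow if that wording is applied to maintenance:
- An abnormality that starts in induction and persists is counted as a new maintenance shift.
- A patient who is high at screening, normalises in induction and becomes high again in maintenance is left out of the shift-to-high count, because that count admits only patients whose baseline maximum was normal or low. Such patients can be enrolled: inclusion criterion 11b allows ALT and AST up to 2 × ULN.

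Weight gain is also judged from the screening-period maximum. With assumed gains of 6% in induction and then 1%, 1.06 × 1.01 = 1.0706. This passes the 7% threshold in SAP Table 5 as a maintenance event, although the gain since the end of induction is 1%. The two percentages are illustrative and do not come from the documents.

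**The case against.** Four points can fairly be made for the plan.

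**A pre-treatment baseline is legitimate.** Change since before any study drug is an interpretable cumulative summary, and Protocol 12.2.1 lets changes that are not principal features be described in the clinical study report. This stands. What is missing is a statement that the SAP chose this, and a label that tells the reader so.

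**The comparison between regimens is safe.** A reader might infer that the Q4W versus Q12W contrast is biased. It is not, in expectation (step 4). At most, its precision and interpretation change.

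**Screening period may simply mean everything before the first dose.** A reader might infer three contradictory baselines, with the laboratory baseline up to 28 days earlier than Visit 2. The documents do not establish that. The SAP revision history says that baseline period was renamed screening period throughout. SAP 6.14.8.2 counts all values up to first dose as screening, though only for immunogenicity. The Table 9 footnote uses the randomisation date for both terms, though only for protocol deviations. On the other side, Attachment 1 labels Visit 1 screening and Visit 2 baseline, with chemistry and haematology at both. The version 3 log also records a clarification of the vital-sign baseline, while 6.14.4 kept its own wording. The laboratory rule is therefore ambiguous, not shown to be contradictory.

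**The reset for former placebo patients still applies.** A reader might infer that 6.14.4 cancels it for laboratory data. SAP 6.14 applies the reset to all quantitative safety analyses, and nothing in 6.14.4 withdraws it.

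**Conclusion.** The conflict over the maintenance baseline is explicit: Week 0 in SAP 6.14, the last induction value in Protocol 12.2.8, and no declaration in SAP 6.18. If the SAP is followed, within-arm maintenance changes in laboratory values, vital signs and weight include 11 to 12 weeks of induction change. Maintenance shift and treatment-emergent counts are made against pre-induction extremes and can err in both directions. If the protocol is followed, neither problem arises.

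The size in clinical units cannot be derived, because the documents give no expected induction change for any safety variable. The conclusion assumes only the nominal visit days and that the SAP text would be programmed as written. No efficacy result depends on it, and the randomised safety contrast between regimens is unbiased in expectation. The laboratory wording is a separate, smaller matter of ambiguity. The point should be fixed because it is cheap and because maintenance safety will be read largely within arm.

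**What to change.** In SAP 6.14, state one baseline per period:
- **Induction:** last value on or before first dose, pre-dose Visit 2 included.
- **Maintenance:** last induction value, as in the protocol.
- **Extension, former placebo patients:** last value on or before first dose at Extension Visit 1, as 6.14 already says.
- **Extension, patients who had LY3074828 in induction:** say explicitly which baseline applies. At present they keep Week 0 by default.

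Align 6.14.4 and 6.14.5 with this. In 6.14.4, replace the screening-period wording in the two sentences that define baseline as the last observation. Do not delete the minimum and maximum baselines in 6.14.4, 6.14.4.1 and 6.14.5, which are deliberate. Keep them and define the baseline window for each period.

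If Week 0 is what the sponsor wants for maintenance, declare it in 6.18 and label those summaries as cumulative change since before induction.

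The cost is SAP wording and the matching derivation programs. No new data are needed, since the Visit 7 values are already scheduled.

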6.14.1. Extent of Exposure

6.14.1.1. Duration of Exposure

Duration of exposure to study treatment (defined as time since first injection of study treatment in days) will be summarized by treatment group during the Induction Period, the Maintenance Period, the Extension Period.

Duration of exposure during the Induction Period for the Safety Population will be calculated as:

(Disposition date (for those who have discontinued the Induction Period), OR Maintenance/Extension Start date -1 (for those who have completed the Induction Period), OR Date of last study visit in the Induction Period (for those who are still being treated in the Induction Period) – Date of first injection of study treatment + 1)

Duration of exposure during the Maintenance Period will be calculated as:

(Disposition date (for those who have discontinued the Maintenance Period), OR Date of last study visit in the Maintenance Period (for those who are still being treated in the Maintenance Period) – Date of the Visit 8 injection of study treatment + 1)

Duration of exposure to LY3074828 during the Extension Period will be calculated as:

(Disposition date (for those who have discontinued the Extension Period), OR Date of last study visit in the Extension Period (for those who are still being treated in the Extension Period) – Date of the Extension Visit 1 injection of study treatment + 1)

Duration of exposure to LY3074828 for the combined Induction Period and Maintenance Period will be calculated as:

(Disposition date (for those who have discontinued the Maintenance Period), OR Date of last study visit in the Maintenance Period (for those who are still being treated in the Maintenance Period)– Date of first injection of LY3074828 + 1)

Duration of exposure to LY3074828 for the combined Induction Period and Extension Period will be calculated as:

(Disposition date (for those who have discontinued the Extension Period), OR Date of last study visit in the Extension Period (for those who are still being treated in the Extension Period)– Date of first injection of LY3074828 + 1)

The date of first injection of LY3074828 is defined in Table 4.

Table 4 First Injection of LY3074828 by Treatment Group

	Visit of first LY3074828
All patients randomized to LY3074828 (regardless of Week 12 response status)	Week 0 (Visit 2)
Week 12 Inadequate Responders originally randomized to placebo and assigned to LY3074828 at Extension Visit 1	Extension Week 0 (Visit EV1)

Descriptive statistics will be provided for patient days of exposure and the frequency of patients falling into the following different exposure ranges (that is, only the exposure ranges that fall within the treatment period will be presented) will be summarized:

- >0, ≥7 days, ≥14 days, ≥30 days, ≥60 days, ≥90 days, ≥120 days, ≥183 days, ≥365 days, ≥548 days.
- >0 to <7 days, ≥7 to <14 days, ≥14 to <30 days, ≥30 to <60 days, ≥60 to <90 days, ≥90 to <120 days, ≥120 to <183 days, ≥183 to <365 days, ≥365 days to <548 days, and ≥548 days

Additional exposure ranges may be considered if necessary.

A by-patient listing of exposure duration will be provided.

Patients who had dose modification will be grouped under the randomized treatment arm and will not be grouped by the modified dose amount.

No inferential analysis for comparison between treatment arms will be performed.

6.14.1.2. Total Dose of active study treatment

The total number of active injections of LY3074828 will be summarized by LY3074828 treatment group.

Mean and median total dose will be reported for all the treatment groups.

Total dose of active study treatment during the Induction Period, the Maintenance Period, the Extension Period, the combined Induction Period and Maintenance Period and the combined Induction Period and Extension Period will be summarized by active treatment group using descriptive statistics. The total dose (mg) will be calculated as:

Total Dose = Sum over all injections received of [dose of LY3074828 (mg) prescribed per injection]

The injections received during the treatment periods will be identified using the response to the question "Was study drug administered to patient?" on the Study administration eCRF page. The total dose of LY3074828 will then be calculated for each treatment group based on the injection schedule using Attachments 1 and 2 in the study protocol.

Patients who had dose modification will be grouped under the randomized treatment arm and will not be grouped by the modified dose amount.

No inferential analysis for comparison between treatment arms will be performed.

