9.5. Therapeutic Drug Monitoring and Dose Adjustment

Experience with use of anti-TNF antibodies in treating IBD suggests that inadequate drug exposure in some subjects may be a factor contributing to lack of efficacy (Ordás et al. 2012b). The application of therapeutic drug monitoring and dose adjustment may therefore result in a higher probability of response in individual subjects who have low exposure and improved overall response rates.

Exposure-Based Dose Adjustment

In this study, subjects in the 50- and 200-mg dose groups will have their doses increased at the Week 4 (Day 29) and Week 8 (Day 57) visits if the projected trough concentrations for those visits fall below prespecified thresholds. The concentration thresholds selected for the 50- and 200-mg arms are 0.5 and 2.0 µg/mL, respectively. The concentrations of 0.5 and 2.0 µg/mL are not related to expected efficacy at these specific target concentrations but rather were selected so that only the subjects with lower than expected exposures in the 50- and 200-mg groups would have their doses increased. On the basis of PK simulations, these thresholds are estimated to result in dose increases in approximately 40% of subjects at Week 4. A smaller percentage of subjects are expected to require dose adjustment at Week 8.

The projected trough concentration for an individual subject will be estimated on the basis of concentration data collected before the date when doses will be adjusted. Application of exposure-based dose adjustment in this study will only serve to increase the dose level if drug concentrations are below the prespecified thresholds. Dose level will not be reduced on the basis of drug concentrations, and once a subject has a dose level increase, the dose will not be reduced. Dose adjustments on the basis of drug concentration levels will only be done during the induction period.

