- e Blood pressure and heart rate should be measured after the subject has been supine for at least 5 minutes. If orthostatic measurements are required, subjects should be supine for at least 5 minutes and stand for at least 3 minutes.
- f All subjects should be monitored for 1 hour after dosing or longer according to investigator practice/local standard of care.
- g See Section 10.1.4 for a description of the endoscopy procedures.
- h See Section 10.3.2.2 for detailed description of QuantiFERON-TB Gold and PPD T-SPOT testing. PPD should be read approximately 48 to 72 hours after placement and response recorded in mm of induration.
- i ECGs should be performed before any blood is drawn. Subjects should be supine for approximately 5 to 10 minutes before ECG collection and remain supine but awake during ECG collection.
- j To be performed only for women of childbearing potential.
- k FSH test is to be performed at screening for women who have had spontaneous amenorrhea for 6 to 12 months to confirm lack of childbearing potential.
- l On the day of dosing, PK samples should be drawn before each intravenous infusion (trough) and at the end of the infusion (C_{max}).
- m MMP-9 and NGAL as blood biomarker in addition to fecal calprotectin as quick response marker of LY3074828 treatment.
- n A single sample is to be drawn prior to investigational product administration if occurring on a dosing day.
- o See Section 7.1 for a detailed description of the randomization process during the maintenance period.
- p Subjects will not need to undergo an endoscopy/biopsy at the EOS visit if they discontinued the study due to reasons specified in Section 8.3.1.
- q Any enrolled subject who is HBcAb+ will undergo monitoring of HBV DNA according to schedule of events. Any subject with a positive HBV DNA test at any time must be discontinued from the study and receive appropriate follow-up medical care, including consideration for antiviral therapy.
- r An additional PK sample will be drawn 2 to 10 days after the first SC dosing in the maintenance period.
- s Visit V804 (Week 120) will serve as the EOS visit or ET visit if a subject prematurely discontinues from the study at any time during the maintenance or maintenance follow-up period.

**Attachment 2. Protocol I6T-MC-AMAC Extension and
Follow-Up Periods Study Schedule**

**Study Schedule, Protocol I6T-MC-AMAC
Extension Period—Induction (1 of 3)**

	Extension Period - Induction					

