Prior Biologic UC Therapy may be summarized using ATC codes L04AA, L04AB, A07E (where preferred name="ETROLIZUMAB"). Prior Biologic use status for the purposes of subpopulation identification will be based on the 'Prior Biologic Y/N?' eCRF question.

TDM adjustment status will be determined by utilizing responses in the Exposure Based Dose Adjustment eCRF page.

Additional subgroup analyses may be performed as deemed necessary.

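### SAP 6.14.1.2 derives total dose from a yes/no flag and a visit schedule that hold no mg amounts; if followed, exposure-based dose increases would be missed

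*SAP*

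**What the plan says.** SAP 6.14.1.2 gives a formula: "Total Dose = Sum over all injections received of [dose of LY3074828 (mg) prescribed per injection". It then names two sources. Injections received are identified by the eCRF question "Was study drug administered to patient", and the total is calculated for each treatment group "based on the injection schedule using Attachments 1 and 2 in the study protocol". On adjusted doses it says only: "Patients who had dose modification will be grouped under the randomized treatment arm and will not be grouped by the modified dose amount". Mean and median total dose are reported, with no inferential comparison.

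The dosing rows of Protocol Attachments 1 and 2 contain X marks. The footnote to the row in Attachment 1 reads "All subjects should be monitored for 1 hour after dosing or longer according to investigator practice/local standard of care"; it says nothing about amount.

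Protocol 9.5 makes dose increases part of the design in the 50 mg and 200 mg arms. For Week 4, "these thresholds are estimated to result in dose increases in approximately 40% of subjects at Week 4". For Week 8, "A smaller percentage of subjects are expected to require dose adjustment at Week 8". An increase is not later reversed, and no induction dose may exceed 600 mg.

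SAP 6.15.1 shows that adjustments are captured: "TDM adjustment status will be determined by utilizing responses in the Exposure Based Dose Adjustment eCRF page". SAP 6.14.1.2 does not refer to that page.

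**The concern.** The formula and the derivation point in different directions. The formula needs a mg value for each administration. The two named sources supply only whether a dose was given and when one was due. The only mg value attached to a treatment group as such is its nominal dose (Protocol Table AMAC.1, SAP 5.3). A programmer following the derivation would therefore arrive at nominal dose times the number of infusions given, and one following the formula might use the adjusted dose. The two would produce different tables.

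What is at stake is the reported mean mg in the two adjustable arms. Nominal totals would understate what those arms received and make them look further from the 600 mg arm than they were.

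**Working it through.** **Inputs**
- Three induction infusions (Weeks 0, 4, 8) at nominal dose d = 50 or 200 mg: Protocol Table AMAC.1.
- Share raised at Week 4: 0.40, from Protocol 9.5. Assumed to apply to each of the two arms.
- A Week 4 increase also applies at Week 8, and the cap is 600 mg per administration: Protocol 9.5.
- Share newly raised at Week 8: e. The protocol says only that fewer are expected to need adjustment then, so e is taken as 0, with an upper range to just under 0.40.
- Increased dose D: not given in the visible text, so d < D ≤ 600 mg.
- All three infusions are assumed given, with the same D at Weeks 4 and 8.

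**The plan's own figure.** The 40% comes from PK simulations whose model and variability are not in the documents. It cannot be reproduced and is used as given.

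**Total from flag and schedule.** 3d = 3 × 50 = 150 mg, and 3 × 200 = 600 mg.

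**Mean total with increases counted.** Mean = 3d + 0.40 × 2 × (D − d) + e × (D − d). With e = 0:

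| Arm | Assumed D | Mean total | Nominal | Understated, as % of true mean |
|---|---|---|---|---|
| 50 mg | 75 mg | 150 + 0.8 × 25 = 170 | 150 | 20/170 = 12% |
| 50 mg | 100 mg | 150 + 0.8 × 50 = 190 | 150 | 40/190 = 21% |
| 50 mg | 600 mg (cap) | 150 + 0.8 × 550 = 590 | 150 | 440/590 = 75% |
| 200 mg | 300 mg | 600 + 0.8 × 100 = 680 | 600 | 80/680 = 12% |
| 200 mg | 400 mg | 600 + 0.8 × 200 = 760 | 600 | 160/760 = 21% |
| 200 mg | 600 mg (cap) | 600 + 0.8 × 400 = 920 | 600 | 320/920 = 35% |

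As D approaches d, the understatement approaches 0%. With e just under 0.40, the ceilings rise to about 590 + 0.4 × 550 = 810 mg and 920 + 0.4 × 400 = 1080 mg.

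**Separation from the 600 mg arm** (3 × 600 = 1800 mg). Against the 50 mg arm the nominal ratio is 1800/150 = 12. It would be 1800/190 = 9.5 if increased doses were doubled, and 1800/590 = 3.1 at the cap.

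**Median.** If fewer than half of an arm is ever raised (0.40 + e < 0.50), the median stays at the nominal total even when increases are counted. The mean carries the error.

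**Other periods.** Attachment 1 marks dosing at every visit from V8 (Week 12) to V31 (Week 104), which is 24 marks. A Q12W patient is due active drug at Weeks 12, 24, 36, 48, 60, 72, 84 and 96, which is 8 injections, with placebo at the other visits (Protocol Table AMAC.1). The schedule alone cannot tell 8 × 200 = 1600 mg from 24 × 200 = 4800 mg. Attachment 2 likewise gives no amount, although SAP Table 1 reports both 600 mg and 1000 mg extension induction groups.

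**The case against.** The strongest reply is that the formula governs. After an exposure-based increase, the amount prescribed for that infusion is naturally the increased one, and the yes/no question serves only to count injections. The attachments hold no mg at all, so they supply no nominal dose either; the amount must come from elsewhere, and the section does not say that source is nominal. The sentence on modified patients shows that the authors had individual amounts in mind.

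Much of this stands. A reader might infer that the SAP excludes dose increases from total dose. The documents do not support that: no sentence says so, and the formula can be read the other way. But the grouping sentence does not say which mg value is summed, and the sources named for the calculation cannot deliver an adjusted dose. The section is inconsistent, or at best under-specified.

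A reader might also infer three further things that do not hold:
- That 40% of each arm is raised over the whole of induction. The figure is for Week 4, and the share ever raised is not stated.
- That the cap figures are expected values. The 600 mg is a ceiling, and nothing suggests that every increase would reach it.
- That safety per mg or the biomarker correlations would be wrong. No per-mg safety analysis is planned; exposure-adjusted adverse event rates use person-time (SAP 6.14.2.1, 6.14.3). SAP 6.14.7 refers to dose levels, not total dose.

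Exposure-response is addressed separately by the PK/PD analyses (Protocol 12.2.7, SAP 6.13), and adjustment status is already a planned subgroup.

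**Conclusion.** The point holds as a conflict between a formula and its stated derivation. If the named sources are followed, mean induction total dose is understated in the 50 mg and 200 mg arms. The amount runs from near 0% up to 75% and 35% of the true mean respectively, assuming 40% raised from Week 4, none newly raised at Week 8, all infusions given, and increases anywhere up to the 600 mg cap. Where in that range the truth lies cannot be determined from the documents. The medians may be unaffected.

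The primary analysis and the planned efficacy and safety tests are untouched. The change should still be made, because a reported result, mean mg by arm, depends on which half of the section the programmer follows.

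**What to change.** Replace the schedule-based sentence in SAP 6.14.1.2 with a rule along these lines: total dose is the sum, for each patient, of the recorded mg of LY3074828 at each infusion or injection given, including exposure-based increases and counting placebo injections as zero, taken from the study drug administration and Exposure Based Dose Adjustment eCRF pages. Keep the existing rule that patients are grouped by randomised arm. The same wording settles the Q12W maintenance arm and the two extension doses.

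Before finalising, confirm that those pages hold mg. SAP 6.15.1 cites the adjustment page only for yes/no status. SAP Table 9 treats ineligible adjustments and dose decreases as programmable from the clinical database, which suggests that amounts are available but does not prove it. If neither page holds them, name the record that does.

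The cost is one sentence, one check of the eCRF and a small programming change. If the mg are recorded, no new data are needed.
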